5.2 EXCLUSION CRITERIA

To be enrolled in the study, potential subjects must meet **NONE** of the following exclusion criteria:

Disease-Related

1. Transformed lymphoma; if clinical evidence of transformed lymphoma is present, transformation should be ruled out by biopsy of the suspicious lymph node/lesion
2. Prior treatment for follicular lymphoma or marginal zone lymphoma (Except: involved field or site radiation therapy is allowed)
3. Medically apparent central nervous system lymphoma or leptomeningeal disease
4. Tumor burden where administration of other FDA approved anti-CD20 antibodies like single-agent rituximab would be inappropriate.
5. Patients in need of immediate cytoreduction with chemotherapy based regimen.

Concurrent Conditions

1. Evidence of chronic active Hepatitis B (HBV, not including patients with prior hepatitis B vaccination; or positive serum Hepatitis B antibody) or chronic active Hepatitis C infection (HCV), active cytomegalovirus (CMV), or known history of HIV (or positive HIV test during screening). If HBc antibody is positive, the subject must be evaluated for the presence

of HBV DNA by PCR. If HCV antibody is positive, the subject must be evaluated for the presence of HCV RNA by PCR. See Appendix: HEPATITIS B SEROLOGIC TEST RESULTS. If the subject is CMV IgG or CMV IgM positive, the subject must be evaluated for the presence of CMV DNA by PCR. Subjects with positive HBc antibody and negative HBV DNA by PCR are eligible. Subjects with positive HCV antibody and negative HCV RNA by PCR are eligible (subjects who are CMV IgG or CMV IgM positive but who are CMV DNA negative by PCR are eligible).

2. For subjects with a prior known history of hepatitis B and for those with a positive anti-HBc with negative HBsAg at screening, contraindication or intolerance to antiviral agents effective against hepatitis B.
3. Ongoing drug-induced liver injury, alcoholic liver disease, non-alcoholic steatohepatitis, primary biliary cirrhosis, extrahepatic obstruction caused by stones, or cirrhosis of the liver
4. Inflammatory bowel disease (such as Crohn's disease or ulcerative colitis)
5. Irritable bowel syndrome with greater than 3 loose stools per day as a baseline

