- *Patients with a prior known history of hepatitis B and for those with a positive anti-HBc with negative HBsAg at screening:* Prophylaxis with an antiviral agent effective against hepatitis B is required. Consider consulting clinicians with an expertise in managing subjects with a prior history of hepatitis B regarding monitoring and consideration of options for hepatitis B antiviral therapy for prophylaxis/treatment. Monitor subjects closely as clinically indicated based on liver tests and any observed signs/symptoms such as jaundice, abdominal pain, dyspepsia, dark-colored urine often accompanied by lighter-than-normal colored stools, nausea, vomiting or fatigue.
- *Hypersensitivity and Infusion Reaction Precautions:* Medication and resuscitation equipment must be available per institutional guidelines prior to ublituximab administration for the emergency management of potential anaphylactic reactions.
- *Patient Care Implications:*
 - Ublituximab should not be administered as an IV push or bolus.
 - Ublituximab may be administered on an outpatient basis.
 - Diluted ublituximab should be checked before administration for cloudiness, color, or deposits. Ublituximab should not be administered if does not conform to the specifications. Immediately inform TG Therapeutics, Inc. at [contact] with any product quality concerns or questions.
 - No other treatment may be co-administered with ublituximab (other than for immediate intervention for adverse event).
 - Concurrent glucocorticoid therapy as long as started at least 7 days prior to study entry (≤ 10 mg per day of prednisone or equivalent) is allowed as clinically warranted.
 - Since infusion-related hypotension may occur, **consider holding antihypertensive medications 12-24 hours prior to and throughout infusion of ublituximab.**
Decision to withhold antihypertensive medication is at investigator discretion.

- For patients at risk for tumor lysis syndrome, in the opinion of the treating investigator, prophylaxis with allopurinol or per recommended institutional standards should be considered.

Ublituximab should not be mixed with other medicinal products. Ublituximab should only be diluted in 0.9% NaCl before use. No data are available for other solutions such as 5% dextrose and 5% mannitol.

Ublituximab is available in 150 mg (6 mL quantity vial) and 900 mg (36 mL quantity vial) single use vials as a 25 mg/mL concentrate for dilution. Dilutions for ublituximab are as follows:

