7.2 LABORATORY PROCEDURES/EVALUATIONS

Local laboratory assessments as specified on the schedule of events table will include the following:

- Hepatitis B virus (HBV) testing will include hepatitis B surface antigen (HBsAg), antibody to the hepatitis B surface antigen (anti-HBs), and antibody to the hepatitis B core antigen (anti-HBc). If a subject is anti-HBc or HBsAg positive, a quantitative polymerase chain reaction test to measure viral DNA load will be performed. Interpretation of this test is described in the **Appendix** section
- Testing for HCV (testing for antibody; if positive then quantitative polymerase chain reaction test to measure viral RNA load).
- HIV testing will be performed per institutional guidelines.
- Testing for CMV, If CMV IgG or IgM is reactive, the subject must be evaluated for the presence of CMV DNA (by PCR).
- Hematology: Complete Blood Count (CBC) with absolute differential, including hematocrit, hemoglobin, white blood cell count (WBC) with differential, and platelet count.
- Chemistry: Comprehensive Metabolic Panel including albumin, alkaline phosphatase, alanine aminotransferase (ALT/SGPT), aspartate transaminase (AST/SGOT), bilirubin (total and direct), calcium, chloride, creatinine, glucose, phosphorous, potassium, sodium, total protein, serum urea/blood urea nitrogen (BUN), LDH, Uric acid.
- Serum beta₂-microglobulin.
- Thyroid function tests will include thyroid stimulating hormone (TSH) and free thyroxine (fT4).
- Calculated creatinine clearance (CrCl) will be estimated using the Cockcroft-Gault formula: CrCl (mL/min) = (140 – age) (weight [kg]) / 72 (serum creatinine [mg/dL]; for females, the formula is multiplied by 0.85 (Cockcroft, 1976).
- Coagulation tests will include prothrombin time, international normalized ratio (INR) and partial thromboplastin time (PTT or activated PTT).
- Urinalysis (a urine dipstick may be used) will include color, appearance, specific gravity, pH, glucose, ketones, blood, bilirubin, and protein. A microscopic examination will be performed if urinalysis result is abnormal.

Pregnancy testing will be performed for females of child-bearing potential. A serum pregnancy test must be done \leq 3 days of starting treatment with single agent ublituximab induction.

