- Urinalysis (as outlined in section 7.2)
- TSH and free T4
- PT/INR and PTT
- Serum beta₂-microglobulin
- HIV, HBV, HCV, CMV screen (as outlined in section 7.2)
- Creatinine Clearance
- PET-CT will be performed within 42 days of C1D1 of treatment
- 12-lead single electrocardiogram (ECG) will be recorded.
- Bone marrow biopsy analysis will be performed for patients with FL and MZL within 6 months prior to study registration)
- Subject self-reported health related quality of life will be assessed at Screening using the FACT-Lym questionnaire
- Research blood tubes will be collected for correlative analysis as described in this protocol.

Inclusion/exclusion criteria will be reviewed in detail to ensure that the patient is a study candidate prior to enrollment and subsequent treatment. If it is not clear if patient qualifies for study, the principal investigator should be notified for review of patient candidacy.

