22. Hepatitis B virus (HBV) testing will include hepatitis B surface antigen (HBsAg), antibody to the hepatitis B surface antigen (anti-HBs), and antibody to the hepatitis B core antigen (anti-HBc). If a subject is anti-HBc or HBsAg positive, a quantitative polymerase chain reaction test to measure viral DNA load.
23. Testing for HCV (testing for antibody; if positive then quantitative polymerase chain reaction test to measure viral RNA load), CMV testing by PCR every 3 cycles during treatment. HIV testing will be performed per institutional guidelines.
24. A microscopic examination will be performed if urinalysis result is abnormal.
25. Research samples to be collection prior to C4,C8 and C12 on combination therapy for correlative analysis as described in this protocol
26. 6 months, 12 months, 18 months and 24 months post completion of therapy – last dose of ublituximab (for single agent treatment) and umbralisib (for combination therapy)
27. Subject self-reported health related quality of life (FACT-LYM) will be assessed at screening and at all time-points when a PET CT is performed (i.e EOInduction, Prior to C4,8,12 of combination therapy, EOT, 6,12,18 and 24 months)
28. 4 weeks after last dose of Single agent Induction and Combination therapy patients will be seen in clinic for history and physical exam including vital signs and weight, lab evaluation including CBC and chemistry and AEs and concomitant medications.
29. All laboratory, safety, and physical examinations should be performed by a provider or nurse within 48 hours of the start of every dose.
30. Ublituximab will be administered every cycle (28 days) through Cycle 6, and then every 3 cycles (i.e. at Cycle 9 and Cycle 12).

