Hepatitis B serologic testing involves measurement of several hepatitis B virus (HBV)-specific antigens and antibodies. Different serologic "markers" or combinations of markers are used to identify different phases of HBV infection and to determine whether a patient has acute or chronic HBV infection, is immune to HBV as a result of prior infection or vaccination, or is susceptible to infection.

HBsAg	negative	Susceptible
anti-HBc	negative	
anti-HBs	negative	
HBsAg	negative	Immune due to natural infection
anti-HBc	positive	
anti-HBs	positive	
HBsAg	negative	Immune due to hepatitis B vaccination
anti-HBc	negative	
anti-HBs	positive	
HBsAg	positive	Acutely infected
anti-HBc	positive	
IgM anti-HBc	positive	
anti-HBs	negative	
HBsAg	positive	Chronically infected
anti-HBc	positive	
IgM anti-HBc	negative	
anti-HBs	negative	
HBsAg	negative	Interpretation unclear; four possibilities:
anti-HBc	positive	1. Resolved Infection (most common)
anti-HBs	negative	2. False-positive anti-HBc, thus susceptible
		3. "Low level" chronic infection
		4. Resolving acute infection

Adapted from: A Comprehensive Immunization Strategy to Eliminate Transmission of Hepatitis B Virus Infection in the United States: Recommendations of the Advisory Committee on Immunization Practices. Part I: Immunization of Infants, Children, and Adolescents. MMWR 2005;54(No. RR-16).

■ Hepatitis B surface antigen (HBsAg):

A protein on the surface of hepatitis B virus; it can be detected in high levels in serum during acute or chronic hepatitis B virus infection. The presence of HBsAg indicates that the person is infectious. The body normally produces antibodies to HBsAg as part of the normal immune response to infection. HBsAg is the antigen used to make hepatitis B vaccine.

■ Hepatitis B surface antibody (anti-HBs):

The presence of anti-HBs is generally interpreted as indicating recovery and immunity from hepatitis B virus infection. Anti-HBs also develops in a person who has been successfully vaccinated against hepatitis B.

■ Total hepatitis B core antibody (anti-HBc):

Appears at the onset of symptoms in acute hepatitis B and persists for life. The presence of anti-HBc indicates previous or ongoing infection with hepatitis B virus in an undefined time frame.

■ IgM antibody to hepatitis B core antigen (IgM anti-HBc):

Positivity indicates recent infection with hepatitis B virus (≤ 6 mos). Its presence indicates acute infection.

DEPARTMENT OF HEALTH & HUMAN SERVICES

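### The hepatitis B eligibility sentence omits HBsAg, so read literally it can admit an HBsAg-positive patient whom the serology-based hepatitis B safeguards do not cover

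*Combined protocol and SAP*

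**What the plan says.** Section 5.2, Concurrent Conditions, item 1 opens by excluding "Evidence of chronic active Hepatitis B (HBV, not including patients with prior hepatitis B vaccination; or positive serum Hepatitis B antibody". It does not define chronic active disease and does not mention HBsAg. The item requires HBV DNA testing when anti-HBc is positive, points to the hepatitis B serology appendix, and then says "Subjects with positive HBc antibody and negative HBV DNA by PCR are eligible".

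Item 2 adds an exclusion for patients who cannot take hepatitis B antivirals. It applies where earlier hepatitis B is already known, and its serology limb reads: "with a positive anti-HBc with negative HBsAg at screening, contraindication or intolerance to antiviral agents effective against hepatitis B".

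HBsAg is measured at screening. Section 7.2 says what follows from a positive result: "If a subject is anti-HBc or HBsAg positive, a quantitative polymerase chain reaction test to measure viral DNA load will be performed". Footnote 22 of the Schedule of Events (7.4) gives the same instruction. Neither says that a positive HBsAg excludes.

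Section 6.1 requires antiviral prophylaxis for "Patients with a prior known history of hepatitis B and for those with a positive anti-HBc with negative HBsAg at screening", and section 7.7 repeats this. Section 6.1.2 uses nearly the same definition for its rule that ublituximab is held at once, and active hepatitis B looked for, when liver enzymes rise. The footnotes to Tables 2 and 3 refer back to that rule.

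The hepatitis B appendix states: "The presence of HBsAg indicates that the person is infectious".

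**The concern.** The eligibility sentence uses two markers, anti-HBc and HBV DNA. The safeguards use anti-HBc and HBsAg. The two definitions do not match, and the patients who fall between them are HBsAg-positive.

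The result is the wrong way round. A patient with anti-HBc and no HBsAg must receive antiviral prophylaxis and has ublituximab held at any liver-enzyme rise. A patient with anti-HBc and HBsAg, whom the appendix regards as infected, is owed neither by serology. Section 6.1.2 itself provides for hepatitis B reactivation on treatment, and the schedule lists hepatitis B testing at screening only, so no routine repeat test would reveal it.

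**Working it through.** The plan states no figure to reproduce here. The check sets the eligibility rule against the safeguard rule for every serologic profile.

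**Rules as written**
- Eligible under item 1: anti-HBc positive and HBV DNA negative.
- Covered by the safeguards: prior history of hepatitis B, or anti-HBc positive with HBsAg negative.

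**Profiles that meet the eligibility sentence (anti-HBc positive, DNA negative)**

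| HBsAg | Known history | Eligible as written | Covered |
|---|---|---|---|
| Negative | No | Yes | Yes, by serology |
| Negative | Yes | Yes | Yes, by serology and history |
| Positive | Yes | Yes | Yes, by history only |
| Positive | No | Yes | **No** |

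The uncovered profile is the patient whose HBsAg is first found positive at screening.

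**Appendix patterns**
- 6 in all. Anti-HBc-positive: immune by natural infection, acutely infected, chronically infected, unclear = 4.
- Of these 4, HBsAg-negative (natural infection, unclear) = 2; HBsAg-positive (acute, chronic) = 2.
- IgM anti-HBc separates the acute from the chronic pattern and is not in the section 7.2 panel.

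**Where the serology trigger requires negative HBsAg:** 5.2 item 2; 6.1; the 6.1.2 ublituximab rule; the Table 2 footnote; the Table 3 liver-injury footnote; 7.7. That is 6 places, of which the two table footnotes are cross-references to the 6.1.2 rule.

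**The history trigger.** Sections 5.2, 6.1 and 7.7 require a prior *known* history, which does not fit a first detection at screening. The 6.1.2 rule says prior history without *known*, so its application is arguable.

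**Dosing at a Grade 1 or first Grade 2 liver-enzyme rise**
- Anti-HBc positive, HBsAg negative: ublituximab is held at once and the patient is assessed for active hepatitis B.
- Anti-HBc positive, HBsAg positive, no known history: Table 2 keeps the ublituximab dose unchanged in induction, and Table 3 keeps it at full dose and schedule in combination.

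**Possible exposure to ublituximab**
- Induction: 4.
- Combination: cycle 1, 3 doses; cycles 2 to 6, 5 doses; cycles 9 and 12, 2 doses. 3 + 5 + 2 = 10.
- Maximum: 4 + 10 = 14, plus 12 cycles of umbralisib, if the patient has no CR after induction and completes treatment.

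**The case against.** The strongest reply is that the sentence is not a free-standing rule of admission. It sits inside an exclusion, beside parallel sentences for hepatitis C and CMV, and says only that antibody positivity does not exclude once PCR is negative. A patient must still meet none of the exclusions, and an HBsAg-positive patient could be judged to have chronic active hepatitis B, particularly as the same item points to an appendix that labels both HBsAg-positive patterns as infected. The repeated negative-HBsAg wording elsewhere suggests that HBsAg-positive patients were never expected on study.

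There are also general protections. Section 5.2 excludes severe or uncontrolled conditions that could affect participation. Section 7.3.1 says "If it is not clear if patient qualifies for study, the principal investigator should be notified for review of patient candidacy". Section 6.1.2 allows dosing only when laboratory values are acceptable, and section 7.7 refers prophylaxis generally to institutional guidelines. Table 3 calls for assessment of viral infections and a viral hepatitis check before steroids.

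Much of this stands as mitigation, and it makes actual harm unlikely. It does not close the gap:
- Chronic active is undefined and does not clearly include the acutely infected pattern.
- The appendix interprets serology but sets no eligibility rule.
- Item 1 names a positive HIV test at screening as exclusionary and has no counterpart for HBsAg.
- Referral to the principal investigator depends on someone seeing doubt where a sentence says the patient is eligible.
- The general dosing and liver rules rest on discretion. Table 3 does not apply in induction. None of them replaces mandatory prophylaxis or the immediate hold.

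If HBsAg-positive patients were meant to be excluded, that condition was assumed and never written. If they were meant to be eligible, the safeguards are too narrow. The text needs correcting in either case.

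**Conclusion.** The concern holds. Followed as written, the criteria can enrol an HBsAg-positive, anti-HBc-positive, DNA-negative patient with no known history of hepatitis B. That patient falls outside the serology trigger of all three hepatitis B safeguards. Two of the four anti-HBc-positive patterns in the appendix are in this position. These counts describe the rules, not the risk: the documents give no rate for this profile, and none or one among 24 to 30 patients is an assumption.

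The conclusion rests on a literal reading of item 1 and on the serology triggers alone; a careful investigator might exclude the patient. Confidence is medium for that reason. It should be fixed because the possible harm is serious and the correction is easy. The primary endpoint, sample size, type I error and power are unaffected.

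**What to change.** In section 5.2, Concurrent Conditions, item 1, add a positive HBsAg at screening as an exclusion, and add negative HBsAg as a third condition in the eligibility sentence, alongside positive anti-HBc and negative HBV DNA.

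If the sponsor intends HBsAg-positive, DNA-negative patients to be eligible, leave item 1 open to them and instead change the serology trigger to anti-HBc positive or HBsAg positive at screening. That change is needed in 5.2 item 2, 6.1, the ublituximab rule in 6.1.2, the footnotes to Tables 2 and 3, and 7.7. The choice belongs to the sponsor and its medical experts.

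Either change is wording only. HBsAg, anti-HBc and, where triggered, HBV DNA are already collected at screening. The likely cost of the first option is at most one more screen failure, against a screening allowance of 30 − 24 = 6 for screen failures and drop-outs.

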6. Active autoimmune disease requiring ongoing immunosuppressive therapy including systemic corticosteroids (prednisone or equivalent ≤ 10 mg daily allowed as clinically warranted) within 12 months prior to enrollment. Patients are allowed to use topical or inhaled corticosteroids or levothyroxine for hypothyroidism or hypoglycemic agents for diabetes mellitus.
7. Any severe and/or uncontrolled medical conditions or other conditions that could affect participation in the study such as:
 - Symptomatic, or history of documented congestive heart failure NYHA (New York Heart Association) functional classification III-IV [see Appendix: New York Heart Association Classifications]
 - Significant cardiovascular disease such as uncontrolled or symptomatic arrhythmias, CHF, or myocardial infarction within 6 months of enrollment.
 - Concomitant use of medication known to cause QT prolongation or torsades de pointes should be used with caution and at investigator discretion.
 - Poorly controlled or clinically significant atherosclerotic vascular disease including cerebrovascular accident (CVA), transient ischemic attack (TIA), angioplasty, cardiac or vascular stenting within 6 months of enrollment.
7. Women who are pregnant or lactating
8. Live virus vaccines within 4 weeks prior to ublituximab therapy, or planned administration of live virus vaccines during ublituximab therapy
9. History of other malignancies (including myelodysplastic syndromes) **except:**
 - malignancy treated with curative intent and with no known active disease present for >2 years before the first dose of study drug and felt to be at low risk for recurrence by treating physician
 - adequately treated non-melanoma skin cancer without evidence of disease
 - adequately treated carcinoma in situ without evidence of disease

- localized prostate cancer and PSA <1.0 mg/dL on 2 consecutive measurements at least 3 months apart with the most recent one being within 4 weeks of study entry

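### The PSA limit in the localized prostate cancer exception is printed in mg/dL, which makes the numeric threshold inert as written

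*Combined protocol and SAP*

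**What the plan says.** Section 5.2 of the combined protocol and SAP opens by stating that "potential subjects must meet NONE of the following exclusion criteria". Under Concurrent Conditions, item 9 is "History of other malignancies (including myelodysplastic syndromes) except", followed by a short list of exceptions. The last of these is "localized prostate cancer and PSA <1.0 mg/dL on 2 consecutive measurements at least 3 months apart". A further timing condition applies to the later value, which must fall in the final four weeks before the patient enters the trial.

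The rule is an exception to an exclusion, so a patient who meets the PSA limit stays eligible. PSA is mentioned nowhere else in the supplied text. It is absent from the laboratory list in Section 7.2 and from the schedule in Section 7.4, so nothing elsewhere restates or corrects the unit.

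**The concern.** A PSA limit is there to separate patients with low values from the rest. The timing rule, with two values at least three months apart and the later one recent, shows that this limit was meant to do some work. It can do so only if some realistic value could fail it.

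The other exceptions in item 9 each require that the earlier cancer is no longer active or evident. The prostate exception has no such condition, and PSA is its only numeric measure. If the number cannot fail anyone, that part of the exception has no content.

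What is at stake is a clear, auditable eligibility rule. Take a patient with localized disease and a PSA of 4 ng/mL on both occasions. That patient is eligible under the printed unit, but would not be if the same number were meant in ng/mL. An investigator and a monitor could disagree about that patient, and the protocol has no text to settle it.

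**Working it through.** The limit is a printed threshold, not a derived figure, so there is no calculation in the plan to reproduce. The check is a unit conversion.

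**Inputs**
- Printed limit: below 1.0 mg/dL (Section 5.2, item 9).
- Direction: meeting the limit keeps the patient eligible (same item).
- Assumption: laboratories report PSA in ng/mL. The documents do not say this.
- Assumption: PSA values between 0.1 and 1,000 ng/mL. The documents give no distribution, so a wide range is used.

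**Conversion**
- 1 mg = 1,000,000 ng and 1 dL = 100 mL.
- 1.0 mg/dL = 1,000,000 / 100 = 10,000 ng/mL.
- In the other direction, PSA in mg/dL = (PSA in ng/mL) × 100 / 1,000,000.

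**Which values would fail the printed limit**

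| PSA (ng/mL) | Same value (mg/dL) | Below 1.0 mg/dL? | Limit ÷ value |
|---|---|---|---|
| 0.1 | 0.00001 | yes | 100,000 |
| 1 | 0.0001 | yes | 10,000 |
| 4 | 0.0004 | yes | 2,500 |
| 10 | 0.001 | yes | 1,000 |
| 20 | 0.002 | yes | 500 |
| 100 | 0.01 | yes | 100 |
| 1,000 | 0.1 | yes | 10 |

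No value in the range fails. The printed limit is 10,000 times looser than the same number in ng/mL.

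**Does anything statistical depend on it?** Section 10.1 plans 24 patients, a null rate of 30%, an alternative of 50%, a one-sided type I error of 0.10 and 73% power. With an exact binomial rule of at least 11 complete responses in 24, the type I error is 0.074 and the power is 0.729, which agrees with the stated 73%. The screening number also reproduces: 24 / (1 − 0.20) = 30. PSA enters neither calculation.

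**The case against.** The strongest reply is that this is an obvious slip that would do no harm in use. A coordinator with a laboratory report in ng/mL would compare the reported number with 1.0 or query the unit. Few would convert to mg/dL and enroll on that basis. The study has one site, and Section 7.3.1 requires a detailed review of the criteria and refers unclear cases to the principal investigator. Other barriers remain:

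- the disease must be localized;
- two values at least three months apart are needed, one of them recent;
- the Section 5.2 exclusion for severe or uncontrolled conditions applies;
- Section 7.6 bars concurrent anti-neoplastic therapy.

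All of this stands, and it limits the practical effect. It does not make the printed threshold correct.

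A reader might also infer that the trial's results are at risk. The documents do not support that:

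- **Primary endpoint.** One patient is 1/24 = 4.2% of the planned sample, but that is the weight of any patient and not a bias. Nothing in the plan shows that a second cancer changes lymphoma response, and no rate of misapplication can be derived. The denominator is also not fixed at 24, because Section 10.3 analyses all enrolled subjects and Section 10.5 allows 24 to 30.
- **PET reading.** Section 7.1.1 counts focal uptake only where it fits lymphoma. It also provides for biopsy or an interval scan when a new lesion is uncertain, and has a separate score for new uptake unlikely to be lymphoma.
- **PFS and OS.** Both are exploratory (Sections 3 and 10.4.10), with no hypothesis test planned on them.

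Finally, one might read item 9 as opening the trial to active prostate cancer in general. That goes too far. Only the numeric limit is inert, and the barriers above still apply. That the prostate exception was meant to match its neighbours on disease activity is an inference, not something the protocol states.

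**Conclusion.** The point holds as a minor eligibility correction. As printed, the limit equals 10,000 ng/mL and excludes no one across an assumed range of 0.1 to 1,000 ng/mL. The conversion is exact. That the limit has no effect in practice rests on the assumed range. That the unit is a slip for ng/mL is the likely explanation, but it rests on how PSA is usually reported and not on the documents.

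The number of patients affected cannot be estimated from the documents and is probably small. The sample size, the power and the primary analysis are unaffected.

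**What to change.** The sponsor-investigator should confirm the intended PSA unit and the intended numeric limit, and correct Section 5.2, item 9 accordingly. This review does not propose the limit. The confirmed unit should also be used in the eligibility checklist and, where PSA is captured, in the eCRF range check, since Section 14.1 describes automatic range checks and one built on the printed unit would not flag any value in the range above.

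The cost is a short edit to one criterion, made through the usual amendment review, and an update to the eligibility form. No procedure, visit or sample size changes.
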